#### **14.6 Core Laboratory for Evaluation**

Independent central core laboratories or expert physician(s) will conduct objective evaluations of remote monitoring tracings, Holter, Cerebral MRI, endoscopy and will evaluate PV stenosis of all subjects enrolled in Wave I (independently of symptoms) and symptomatic subjects of Wave II.

### 14.7 Schedule of Events Table

Table 5 displays the required schedule for subject treatments and evaluations.

**Table 5: Summary of Subject Visits and Assessments**

Assessments	Pre-Procedure	Pre-Discharge	Follow-up					UNS
			7 Day	1 Month	3 Month	6 Month	12 Month	
Study Day			D7	D30	D90	D180	D365	
Visit window			D7-D9	D23-D37	D76-D104	D166-D194	D335-D379	
Clinic visit	●	●	(●)	●	●	●	●	● 
Phone call			●					
Patient Informed Consent 	●							
Demographics	●							
Medical History 	●							
Pregnancy test 	●							
LA and LVEF assessment 	●							
Left atrial thrombus detection 	●							
Pericardial fluid assessment		●						
12 Lead ECG 	●	●		●	●	●	●	● 
Atrial Arrhythmia monitoring (Remote) 					●	●	●	● 
Atrial Arrhythmia monitoring (24 hour Holter) 					●	●	●	● 
Repeat ablations 			●	●	●	●	●	● 
Concomitant Medication 		●	●	●	●	●	●	● 
Device Deficiencies		●						
Adverse Events 	●	●	●	●	●	●	●	● 
AFEQT 	●				●	●	●	
Cardiac CT/MRA	●				● 			
Wave I subjects ONLY additional assessments								
Endoscopy		● 						
Cerebral MRI 	● 	● 		● 	● 	● 	● 	● 
Neurological Exam 	● 	● 		● 	● 	● 	● 	● 
NIH Stroke Scale 	● 	● 		● 	● 	● 	● 	● 
mRS	● 			●	● 	● 	● 	● 
MMSE 	● 			●	● 	● 	● 	● 

1. Procedure must be done within 60 days of consent.
2. Medical history-including but not limited to arrhythmia, AAD therapy failure, heart disease (NYHA), vital signs, CHA2DS2score and thromboembolic events.
3. In all women of childbearing age and potential. To be completed within 72-hours prior to ablation procedure.
4. Imaging within 6 months prior to procedure to assess the LA and LVEF, in case the imaging assessment is older than 6 months, LA/LVEF dimensions shall be re-measured during the index procedure prior to insertion of the study catheter.

5. Performed the day before procedure or day of ablation procedure to rule out the presence of atrial thrombus using one of the following modalities TEE, ICE, CT, MRI.
6. If Standard of care assessment (For pre-procedure, can be performed before ICF signature)
7. Arrhythmia monitoring via remote monitoring once per week as from 3-month follow-up visit to the end of 5-month follow-up and monthly as of 6-month follow-up visit and whenever subject feels symptoms.
8. Arrhythmia monitoring via 24H Holter, site to contact subject and verify if any symptoms experienced during the Holter monitoring.
9. Information on any repeat ablation after the index procedure will be collected
10. Concomitant medication: only cardiac (i.e. anti-arrhythmia drugs, anticoagulation regimen) & index procedure related (i.e. adenosine, pain medication)
11. AEs must be collected from the time the subject signs the informed consent onward.
12. To be completed within 6 months prior to ablation procedure, For Wave I subjects: CT-MRA to be repeated at 3M FU. For Wave I and Wave II subjects, CT-MRA to be repeated post procedure in case subject presents with PV stenosis symptoms.
13. Endoscopy preferable prior to discharge and no later than 72-hours after procedure. For procedures on Friday a window of a maximum of 96 hours is justified.
14. If observations are noted on the post-procedure MRI, the subject must have follow-up MRI at the next follow-up visit(s) until observations are resolved.
15. A certified/qualified physician expert must perform neurologic exams at pre-and post-ablation and possibly at other follow-up visits, pending previous findings of micro-emboli/neurologic deficits.
16. To be completed within 72-hours pre-procedure. For procedures on Monday a window of a maximum of 96 hours is justified.
17. To be completed within 72-hours post-procedure. For procedures on Friday a window of a maximum of 96 hours is justified.
18. Full neurological follow up to be undertaken if neurologic symptoms and/or cerebral ischemic lesions identified in a prior evaluation.
19. If subject returns for a potential study related cardiovascular or neurological visit outside of the protocol-defined visit schedule as deemed required per investigators discretion.
20. Patient questionnaires will only be used in countries with validated languages.

## 15. Assessment of Safety

### 15.1 Specific Safety Parameters

Pursuant MDR 2017/745, in the occasion relevant (local) regulations, guidance(s) and processes on safety determinations, definitions and reporting become in full force during the course of the study, the Sponsor shall adhere to the applicable definitions and processes.

#### 15.1.1 Definition of Adverse Events (AE)

An AE is any untoward medical occurrence in a subject whether or not related to the investigational device.

Specifically, an AE is **any** undesirable experience (sign, symptom, illness, abnormal laboratory value, or other medical event) occurring to a subject during the course of the study, whether or not it is related to the investigational device or procedure. Physical findings (including vital signs) observed at follow-up, or pre-existing physical findings that worsen compared to baseline are considered AEs.

[figure not shown]
Any medical condition that is present at the time that the participant is screened will be considered as baseline and not reported as an AE. Such conditions should be added to background medical history, if not previously reported. However, if the study participant's condition deteriorates at any time during the study, it will be recorded as an AE.

#### Following arrhythmia's do not meet the definition of an AE:

- AF recurrence by itself is considered a recurrence of disease (pre-existing condition)
- Recurrence of pre-existing or underlying (treated during index procedure) AFL/AT is considered as a recurrence of disease
- Onset of non-previously identified AFL/AT which was treated during the index procedure as underlying arrhythmia (pre-existing condition)
- Re-ablation for AF or any pre-existing AFL/AT, however any procedural complication is considered an AE and shall be reported within the applicable timelines.
- Re-ablation for any non-pre-existing (underlying) AFL/AT which was treated during the index procedure, however any procedural complication is considered an AE and shall be reported within the applicable timelines.
- Cardioversion (pharmacological or synchronized electrical) for AF/AFL/AT recurrence during the hospitalization for the index ablation procedure, or throughout the duration of the study.

#### Following arrhythmia's meet the definition of an AE:

- Onset of non pre-existing AFL/AT which was not treated during the index procedure.

### 15.1.2 Definition of Serious Adverse Event (SAE)

A SAE is any event that meets one or more of the following criteria:

- Leads to a death
- Leads to a serious deterioration in the health of a subject that resulted in:
  - A life-threatening illness or injury
  - An injury or permanent impairment of a body structure or a body function
  - In-patient hospitalization or prolongation of an existing hospitalization\*
  - Medical or surgical intervention to prevent life-threatening illness or injury or permanent impairment to body structure or a body function
  - Chronic disease (MDR2017/745) ☹
- Leads to fetal distress, fetal death or a congenital abnormality or birth defect.

\*Planned hospitalization for a condition present prior to the participant’s enrollment in the study will not meet the definition of an SAE. An AE would meet the criterion of “hospitalization” if the event necessitated an admission to a health care facility (e.g., an overnight stay). Emergency room visits that do not result in admission to the hospital should be evaluated for one of the other serious outcomes.

### 15.1.3 Primary Adverse Event

A **Primary Adverse Event** is an event listed in table 6 which occurs within the first week (7 days) following an ablation procedure.

**Table 6: Primary Adverse Events**

Primary Adverse Event	Description / Criteria
Death*	Subject death directly related to the device or procedure and occurs at any time during or after the procedure.
Atrio-Esophageal Fistula*	Defined as a connection between the atrium and the lumen of the esophagus. Evidence supporting this diagnosis includes documentation of esophagus erosion combined with evidence of a fistulous connection to the atrium such as air emboli, an embolic event, or direct observation at the time of surgical repair. A CT or MRI scan is the most common method of documentation of an AEF.
Myocardial Infarction	Presence of any one of the following criteria: 
 
- Detection of ECG changes indicative of new ischemia (new ST-T changes or new Left Bundle Branch Block [LBBB]) that persist for more than 1 hour
 
- Development of new pathological Q waves on ECG
 
- Imaging evidence of new loss of viable myocardium or new regional wall motion abnormality
 

Primary Adverse Event	Description / Criteria

Cardiac Tamponade**/Perforation
	
The development of a significant pericardial effusion during or within 30 days of undergoing the index AF ablation procedure. A significant pericardial effusion is one that results in hemodynamic compromise, requires elective or urgent pericardiocentesis, or results in a 1cm or more pericardial effusion as documented by echocardiography
 
Cardiac tamponade/perforation should also be classified as:                      Early – diagnosed prior to discharge                      Late – following initial discharge from the hospital

Thromboembolism
	
Formation of a clot (thrombus) inside a blood vessel causing obstruction to blood flow accompanied by clinical symptoms. The thrombus can migrate (embolus) and obstruct distal vascular sites.
 
Diagnostic tests to help detect thromboembolisms may include but are not limited to angiography (pulmonary or distal), ventilation-perfusion (V/Q) scans, venography, Doppler ultrasonography, spiral CT, and echocardiography.
 
For the purpose of this study silent (asymptomatic) cerebral embolism will not be considered a PAE.


Stroke/Cerebrovascular Accident (CVA)
	
Diagnosis:
 
 
-Rapid onset of a focal or global neurological deficit with at least one of the following: change in level of consciousness, hemiplegia, hemiparesis, numbness or sensory loss affecting one side of the body, dysphasia or aphasia, hemianopia, amaurosis fugax, or other neurological signs or symptoms consistent with stroke.
 
-Duration of a focal or global neurological deficit <math>\geq 24</math> h; or <math>< 24</math> h, if therapeutic intervention(s) were performed (e.g. thrombolytic therapy or intracranial angioplasty); OR available neuroimaging documents a new hemorrhage or infarct; or the neurological deficit results in death.
 
-No other readily identifiable non-stroke cause for the clinical presentation (e.g., brain tumor, trauma, infection, hypoglycemia, peripheral lesion, pharmacological influences). †
 
-Confirmation of the diagnosis by at least one of the following: Neurology or neurosurgical specialist; Neuroimaging procedure (MR or CT scan or cerebral angiography); Lumbar puncture (i.e., spinal fluid analysis diagnostic of intracranial hemorrhage).
 
 
Definition:
 
Stroke: (diagnosis as above, preferably with positive neuroimaging study)
 
 
Minor—Modified Rankin score <math>< 2</math> at 30 and 90 days††
 
Major—Modified Rankin score <math>\geq 2</math> at 30 and 90 days
 

Primary Adverse Event	Description / Criteria
Transient Ischemic Attack	New focal neurological deficit with rapid symptom resolution (usually 1 to 2 h), always within 24h; neuroimaging without tissue injury.
Phrenic Nerve Paralysis	Absent phrenic nerve function as assessed by a sniff test. A phrenic nerve paralysis is considered to be permanent when it is documented to be present 12 months or longer following ablation.
Pulmonary Vein Stenosis*	A reduction of the diameter of a PV or PV branch. Severe PV stenosis ( $\geq 70\%$ reduction in the diameter of the PV) will be considered a PAE and major complication of AF ablation.
Major Vascular Access Complication /Bleeding	Major Vascular Access Complication: Development of a hematoma, an AV fistula or a pseudoaneurysm which requires intervention, such as surgical repair or transfusion, prolongs the hospital stay, or requires hospital admission.  Major Bleeding: Requires and/or treated with transfusion or results in a 20% or greater fall in hematocrit.
Pericarditis	Pericarditis should be considered a major complication following ablation if it results in an effusion that leads to hemodynamic compromise or requires pericardiocentesis, prolongs hospitalization by more than 48 hours, requires hospitalization, or persists for more than 30 days following the ablation procedure.

\* Device or procedure related death, atrio-esophageal fistula and pulmonary vein stenosis that occur greater than one week (7 days) post-procedure shall be deemed Primary AE.

\*\* Hemodynamic compromise or instability is defined as Systolic blood pressure < 80 mmHg

† Patients with non-focal global encephalopathy will not be reported as a stroke without unequivocal evidence based upon neuroimaging studies.

†† mRS assessments should be made by qualified individuals according to a certification process. If there is discordance between the 30 and 90 day mRS, a final determination of major versus minor stroke will be adjudicated by an independent physician/committee.

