**CONTACTS:**

Whereas, the Clinical Study is sponsored by Biosense Webster Inc., Johnson and Johnson Medical NV/SA with registered offices at [name], has been duly appointed by the Sponsor to conduct the Clinical Study on its behalf.

The sponsor maintains an updated list of Principal Investigators (PIs), the coordinating investigator (if appointed), address details of each investigational site, emergency contact details for the PI's at each site, roles and responsibilities and qualifications of each respective investigator, institutions,

corelabs (if applicable) and Contract Research Organizations (if applicable). The definitive list shall be integrated into the study report.

The current protocol has been developed based on regulations applicable in Europe, for countries outside Europe, a country specific version of this study protocol may be developed, further defining regional regulations, if applicable.

	
[REDACTED]

Premarket or Post market	Premarket
Study Design	
Prospective, single arm, multi-center, pre-market clinical evaluation of the IRE system (Circular IRE Catheter and IRE Generator) to demonstrate safety and long-term effectiveness when compared to a performance goal based on a historical control.
 
The study shall include two sequential waves:
 
Wave I of the study will enroll up to 40 subjects, who will undergo the index procedure and additional neurological, PV and esophageal assessments.
 
Wave II of the study will enroll roll-ins, and up to 330 subjects in the main phase. Wave II subjects will undergo the index procedure and same follow-up schedule as Wave I subjects, excluding the additional neurological, and post procedural PV (unless symptomatic) and esophageal assessments.
 
Bayesian adaptive design will be used for sample size selection in Wave II of the study.

Sample Size	
As Wave I of the study is a safety characterization phase, a sample size of 40 subjects is intended to delineate safety and provide preliminary estimates for safety and acute effectiveness of the IRE system.
 
Two sample size selection interim analyses will be performed in Wave II. Predictive probabilities of success will be used to determine whether the enrollment will be stopped or continued at each sample size selection interim analysis. The study may enroll up to a maximum of 330 subjects in the main phase.

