1 STUDY DESIGN

This clinical investigation is an interventional, prospective, single arm, multi-center, pre-market clinical evaluation of the IRE ablation system (Circular IRE Catheter and IRE Generator) to demonstrate safety and effectiveness when compared to predetermined performance goals. The study will enroll subjects with drug refractory, symptomatic paroxysmal atrial fibrillation (PAF) who are candidates for catheter ablation in two sequential waves. Wave I subjects will undergo the index procedure and additional neurological, pulmonary vein (PV), and esophageal assessments. Wave II will consist of roll-in and main study phase subjects. Subjects in Wave II will undergo the index procedure and same follow-up schedule as Wave I subjects, excluding the additional neurological, post-procedural PV (unless symptomatic), and esophageal assessments. This statistical analysis plan (SAP) describes the analyses that will be performed for roll-in and main phase subjects in Wave II. A separate SAP describes the analyses for subjects in Wave I.

To verify consistent workflow for study device components and to minimize the learning curve effect on the evaluation of safety and effectiveness of the IRE system, a maximum of 180 roll-in subjects (the first 1-3 subjects for each ablating physician) will be enrolled in the study. The size of the roll-in cohort may be smaller if enrollment in the main study phase terminates at the first sample size interim analysis. Operators who performed procedures in Wave I may be exempt from roll-ins for Wave II per training charter. Roll-in subjects will not be counted towards the enrollment cap of 330 main study subjects.

A Bayesian adaptive design will be used to determine sample size for Wave II. A maximum of 330 main study phase subjects is planned. The number of subjects at any individual site shall not exceed 20% of the total enrollment. All Wave II subjects will be evaluated at 7 days, 1, 3, 6 and 12 months following the index procedure. An additional interim analysis will be performed to claim early trial success.

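### Table 6 has no rule for a transient deficit that was not scanned, and Wave II requires no brain scan, so such an event can be left out of the tested PAE count

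*Protocol*

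**What the plan says.** Stroke and TIA are both components of the primary safety endpoint (Protocol 8.2.1), and Table 6 in Protocol 15.1.3 supplies the criteria. The TIA row reads: "New focal neurological deficit with rapid symptom resolution (usually 1 to 2 h), always within 24h; neuroimaging without tissue injury". In the stroke row, a deficit shorter than 24 hours qualifies through one of three routes. The first is treatment: "if therapeutic intervention(s) were performed (e.g. thrombolytic therapy or intracranial angioplasty". The other two are a positive scan or death: "OR available neuroimaging documents a new hemorrhage or infarct; or the neurological deficit results in death". Thromboembolism is a separate component: "Formation of a clot (thrombus) inside a blood vessel causing obstruction to blood flow accompanied by clinical symptoms". Only silent cerebral embolism is carved out of it.

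Brain imaging and neurological examinations appear in Protocol Tables 1 and 5 under the block "Wave I subjects ONLY additional assessments", and that block includes the unscheduled-visit column. The protocol summary describes Wave II follow-up as the Wave I schedule "excluding the additional neurological, and post procedural PV (unless symptomatic) and esophageal assessments", and section 1 of the Wave II SAP repeats this: "excluding the additional neurological, post-procedural PV (unless symptomatic), and esophageal assessments". Protocol 14.3 requires a cerebral MRI after neurological symptoms in Wave I only. Protocol 14.5 lets an investigator request an unscheduled visit for a neurological deficit in any subject, but requires no scan at it.

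Only Wave II main-phase data are tested. The CEC adjudicates primary safety events in both waves (Protocol 6.4.2).

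**The concern.** The two neighbouring rows treat imaging differently. The stroke row allows for a missing scan by referring to available imaging. The TIA row lists a negative scan as part of the definition and gives no alternative. A focal deficit that clears at home and is first mentioned at the 7-day contact, which may be a phone call, could therefore be a real neurological event that meets no listed criterion.

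The gap falls on the wave that carries the hypothesis test. Wave I subjects have a post-procedure cerebral MRI and neurological examination; Wave II subjects have neither. The documents also treat another imaging-dependent component differently: Wave II subjects with symptoms of PV stenosis must have a CT or MRA, and the symptomatic exception in the study-design text attaches to PV assessment only.

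The study is single-arm with a fixed goal, so an uncounted event is not balanced by a similar loss in a control group. It can only lower the PAE rate.

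**Working it through.** **Step 1: which transient deficits fall between the rows.** For a new focal deficit that resolves within 24 hours, Table 6 gives:

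| Situation | Stroke row | TIA row |
|---|---|---|
| Scan shows new infarct or hemorrhage | can qualify | no |
| Scan shows no tissue injury | only if treated or fatal | yes |
| No scan, therapeutic intervention given | can qualify | not met |
| No scan, results in death | can qualify | not met |
| No scan, untreated, non-fatal | not met | not met |

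Only the last line is the gap.

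**Step 2: how that subject enters the analysis.** A missing safety outcome is defined by follow-up time without a PAE: less than 12 months in Protocol 20.4.4.4, and not reaching 3 months in Wave II SAP 7.4.3. A subject who completes follow-up with an unclassified deficit is therefore an observed non-event. The best-case, worst-case and tipping-point analyses (Wave II SAP 7.4.1.1 and 7.4.1.2) reassign missing outcomes only, so they would not touch this subject.

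**Step 3: reproduce the plan's own safety figures.** Inputs: Beta(1,1) prior and success if Pr(p < 0.14) > 0.975 (Protocol 20.4.4.3; Wave II SAP 7.4.1); true rate 7%, 5% safety dropout, and N = 180, 255 or 330 (SAP Appendix I, 10.2). The cutoff is the largest y with P(Beta(1+y, 1+n−y) < 0.14) > 0.975; power is P(Binomial(n, 0.07) ≤ y), averaged over n ~ Binomial(N, 0.95).

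- Power: 0.825 (N=180), 0.940 (N=255), 0.982 (N=330). This agrees with the stated figure of more than 80%.
- Weighted by the sample-size mix in Table 3.a at 65% effectiveness: 0.5535 × 0.825 + 0.2854 × 0.940 + 0.1611 × 0.982 = 0.883, against a stated safety win rate of 0.8853.

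The decision rule is therefore understood correctly.

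**Step 4: what one event is worth (complete data).**

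| N | Most PAEs that pass (posterior) | One more fails (posterior) |
|---|---|---|
| 180 | 16 (0.9759) | 17 (0.9587) |
| 255 | 24 (0.9832) | 25 (0.9729) |
| 330 | 33 (0.9823) | 34 (0.9733) |

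If exactly k true events go uncounted, the trial passes with k more true events than the cutoff. At a true rate of 14%, the chance of passing is P(Binomial(N, 0.14) ≤ cutoff + k):

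| N | k = 0 | k = 1 | k = 2 |
|---|---|---|---|
| 180 | 2.57% | 4.38% | 7.05% |
| 255 | 1.78% | 2.86% | 4.41% |
| 330 | 1.86% | 2.81% | 4.11% |

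**Step 5: an assumed frequency.** The documents give no rate for unscanned transient deficits. Assume that a share q of subjects has one and is not counted. The counted rate is then 0.14 − q, and the chance of passing is P(Binomial(N, 0.14 − q) ≤ cutoff):

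| N | Expected uncounted, q = 0.25% to 1% | Chance of passing |
|---|---|---|
| 180 | 0.45 to 1.8 | 3.2% to 5.8% |
| 255 | 0.64 to 2.55 | 2.3% to 4.9% |
| 330 | 0.83 to 3.3 | 2.5% to 5.8% |

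**The case against.** The strongest reply is that absence from the research schedule is not absence of work-up. The Wave I scans are marked as outside standard of care. Nothing prevents a Wave II subject with symptoms from being scanned in routine practice, and other Table 6 diagnoses also rely on event-driven tests. The 7-day contact asks about PAEs, every adverse event must be reported, and the CEC adjudicates. An unscanned deficit would still appear in the general adverse-event tables. All of this stands and limits how often the gap can matter. None of it supplies the missing classification rule.

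A reader might go further than the documents allow in four ways:

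- **That every unscanned transient deficit is neither stroke nor TIA.** A treated or fatal one can be a stroke without a scan.
- **That such an event necessarily leaves the PAE rate.** No passage says so. The CEC charter is not among the documents, and the thromboembolism row could take an event if a clot causing obstruction is accepted.
- **That the type I error is really 4.4% or 7.1%.** Those figures apply only if exactly one or two events are missed in a complete N=180 data set. They are not properties of the design, and the simulated 1.72% in SAP Table 3.b describes a different setting that includes dropout.
- **That a Wave II stroke cannot be graded.** Table 6 grades stroke by mRS at 30 and 90 days, and its footnote has no wave limit: "If there is discordance between the 30 and 90 day mRS, a final determination of major versus minor stroke will be adjudicated". Wave II subjects also attend at 1 and 3 months. What remains is that Tables 1 and 5 list mRS for Wave I only. Any qualifying stroke is a PAE whatever its grade, so the test is unaffected.

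A last objection concerns the remedy. Counting every unscanned deficit as a TIA would take in peripheral, metabolic or drug-related deficits, because the TIA row lacks the stroke row's exclusion of other causes. It could also move the composite away from the rates behind the 14% goal (Protocol 6.3). The first part is right, and the fix below carries the exclusion over. The second cannot be settled, because the documents do not say how the source trials classified unscanned events.

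**Conclusion.** The point holds in a limited form. The TIA definition requires a negative scan, the tested wave requires no scan, and no rule covers the case between. An untreated, non-fatal, unscanned transient focal deficit can be left out of the PAE count and treated as an observed non-event. The direction is certain: any omission favours the device. The size is not known. The 2.6% to 4.4% figure assumes one missed event, complete data at N=180 and a true rate of 14%; the 3.2% to 5.8% range rests on an assumed uncounted rate of 0.25% to 1%. The stated safety power reproduces, and no stated power or sample size is wrong. The correction is worth making because a single event can decide the test at the boundary and the change is small. The mRS mismatch is secondary.

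**What to change.** 1. **Table 6, TIA row.** Make the imaging element conditional, so that it requires no tissue injury on neuroimaging if performed.
2. **Table 6, with the same rule in the CEC charter.** State that a new focal deficit that resolves within 24 hours, was not imaged, and has no other readily identifiable non-ischemic cause (the kind of exclusion the stroke row already uses) is adjudicated by the CEC as a TIA and counted as a PAE.
3. **Wave II SAP 7.6.2.** Report these events on a separate line, so that a reader can see the PAE rate with and without them.
4. **Reconcile the mRS passages.** Table 6 presupposes mRS at 30 and 90 days after a stroke, while Tables 1 and 5 list it for Wave I only. This has no effect on the primary test.

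The cost is a sentence or two in Table 6, a matching line in the charter, one table row and one schedule clarification. No scan is added. The PAE rate may come out slightly less favourable.
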